APPENDIX II: TREATMENT OF IMMUNE RELATED REACTIONS

These general guidelines constitute guidance to the Investigator and may be supplemented by discussions with the Medical Monitor representing the Sponsor. The guidance applies to all immuno-oncology agents and regimens.

A general principle is that differential diagnoses should be diligently evaluated according to standard medical practice. Non-inflammatory etiologies should be considered and appropriately treated.

[figure not shown]
Corticosteroids are a primary therapy for immuno-oncology drug-related adverse events. The oral equivalent of the recommended IV doses may be considered for ambulatory patients with low-grade toxicity. The lower bioavailability of oral corticosteroids should be taken into account when switching to the equivalent dose of oral corticosteroids.

Consultation with a medical or surgical specialist, especially prior to an invasive diagnostic or therapeutic procedure, is recommended.

The frequency and severity of the related adverse events covered by these algorithms will depend on the immuno-oncology agent or regimen being used.

GI Adverse Event Management Algorithm

[figure not shown]
Rule out non-inflammatory causes. If non-inflammatory cause is identified, treat accordingly and continue I-O therapy. Opiates/narcotics may mask symptoms of perforation. Infliximab should not be used in cases of perforation or sepsis.

Patients on IV steroids may be switched to an equivalent dose of oral corticosteroids (e.g. prednisone) at start of tapering or earlier, once sustained clinical improvement is observed. Lower bioavailability of oral corticosteroids should be taken into account when switching to the equivalent dose of oral corticosteroids.

Renal Adverse Event Management Algorithm

[figure not shown]
Rule out non-inflammatory causes. If non-inflammatory cause, treat accordingly and continue I-O therapy

Patients on IV steroids may be switched to an equivalent dose of oral corticosteroids (e.g. prednisone) at start of tapering or earlier, once sustained clinical improvement is observed. Lower bioavailability of oral corticosteroids should be taken into account when switching to the equivalent dose of oral corticosteroids.

Hepatic Adverse Event Management Algorithm

Rule out non-inflammatory causes. If non-inflammatory cause, treat accordingly and continue I-O therapy. Consider imaging for obstruction.

[figure not shown]
Patients on IV steroids may be switched to an equivalent dose of oral corticosteroids (e.g. prednisone) at start of tapering or earlier, once sustained clinical improvement is observed. Lower bioavailability of oral corticosteroids should be taken into account when switching to the equivalent dose of oral corticosteroids.

*I-O therapy may be delayed rather than discontinued if AST/ALT \leq 8 x ULN or T.bili \leq 5 x ULN.

**The recommended starting dose for grade 4 hepatitis is 2 mg/kg/day methylprednisolone IV.

Endocrinopathy Management Algorithm

[figure not shown]
Rule out non-inflammatory causes. If non-inflammatory cause, treat accordingly and continue I-O therapy. Consider visual field testing, endocrinology consultation, and imaging.

Patients on IV steroids may be switched to an equivalent dose of oral corticosteroids (e.g. prednisone) at start of tapering or earlier, once sustained clinical improvement is observed. Lower bioavailability of oral corticosteroids should be taken into account when switching to the equivalent dose of oral corticosteroids.

Neurological Adverse Event Management Algorithm

[figure not shown]
Rule out non-inflammatory causes. If non-inflammatory cause, treat accordingly and continue I-O therapy.

Patients on IV steroids may be switched to an equivalent dose of oral corticosteroids (e.g. prednisone) at start of tapering or earlier, once sustained clinical improvement is observed. Lower bioavailability of oral corticosteroids should be taken into account when switching to the equivalent dose of oral corticosteroids.

Skin Adverse Event Management Algorithm

Rule out non-inflammatory causes. If non-inflammatory cause, treat accordingly and continue I-O therapy.

[figure not shown]

Patients on IV steroids may be switched to an equivalent dose of oral corticosteroids (e.g. prednisone) at start of tapering or earlier, once sustained clinical improvement is observed. Lower bioavailability of oral corticosteroids should be taken into account when switching to the equivalent dose of oral corticosteroids.

* Refer to NCI CTCAE v4 for term-specific grading criteria.

^If SJS/TEN is suspected, withhold I-O therapy and refer patient for specialized care for assessment and treatment. If SJS or TEN is diagnosed, permanently discontinue I-O therapy.

MYOCARDITIS ADVERSE EVENT MANAGEMENT ALGORITHM

[figure not shown]

For the protocols under CTCAE version 4.0. Patients on IV steroids may be switched to an equivalent dose of oral corticosteroids (eg, prednisone) at start of tapering or earlier, once sustained clinical improvement is observed. Lower bioavailability of oral corticosteroids should be taken into account when switching to the equivalent dose of oral corticosteroids.

Prophylactic antibiotics should be considered in the setting of ongoing immunosuppression.

ATG = anti-thymocyte globulin; BNP = B-type natriuretic peptide; ECG = electrocardiogram; I-O = immuno-oncology; IV = intravenous; MRI = magnetic resonance imaging

RELATLIMAB MYOCARDITIS ADVERSE EVENT MANAGEMENT ALGORITHM

For the protocols under CTCAE version 5.0. Patients on IV steroids may be switched to an equivalent dose of oral corticosteroids (eg, prednisone) at start of tapering or earlier, once sustained clinical improvement is observed. Lower bioavailability of oral corticosteroids should be taken into account when switching to the equivalent dose of oral corticosteroids. Prophylactic antibiotics should be considered in the setting of ongoing immunosuppression.

ATG = anti-thymocyte globulin; BNP = B-type natriuretic peptide; ECG = electrocardiogram; IV = intravenous; MRI = magnetic resonance imaging

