Suspected adverse reaction: Any adverse event for which there is a reasonable possibility that the drug caused the adverse event. For the purposes of IND safety reporting, "reasonable possibility" means there is evidence to suggest a causal relationship between the drug and the adverse event. Suspected adverse reaction implies a lesser degree of certainty about causality than adverse reaction, which means any adverse event caused by a drug.

Adverse reaction means any adverse event caused by a drug. Adverse reactions are a subset of all suspected adverse reactions where there is reason to conclude that the drug caused the event.

Unexpected adverse event or unexpected suspected adverse reaction: An adverse event or suspected adverse reaction is considered "unexpected" if it is not listed in the investigator brochure or is not listed at the specificity or severity that has been observed; or, if an investigator brochure is not required or available, is not consistent with the risk information described in the general investigational plan or elsewhere in the current application, as amended. For example, under this definition, hepatic necrosis would be unexpected (by virtue of greater severity) if the investigator brochure referred only to elevated hepatic enzymes or hepatitis. Similarly, cerebral thromboembolism and cerebral vasculitis would be unexpected (by virtue of greater specificity) if the investigator brochure listed only cerebral vascular accidents. "Unexpected," as used in this definition, also refers to adverse events or suspected adverse reactions that are mentioned in the investigator brochure as occurring with a class of drugs or as anticipated from the pharmacological properties of the drug, but are not specifically mentioned as occurring with the particular drug under investigation

9.2 POTENTIAL DRUG INDUCED LIVER INJURY IS DEFINED AS:

- 1) An (ALT or AST) elevation > 3 times upper limit of normal (ULN)
AND
- 2) Total bilirubin > 2 times ULN, without initial findings of cholestasis (elevated serum alkaline phosphatase)
AND
- 3) No other immediately apparent possible causes of AT elevation and hyperbilirubinemia, including, but not limited to, viral hepatitis, pre-existing chronic or acute liver disease, or the administration of other drug(s) known to be hepatotoxic.

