12.0 MANAGEMENT OF ADVERSE EVENTS

12.1 IMMUNE RELATED ADVERSE EVENTS

For the purposes of this study, an immune-related adverse reaction is defined as an adverse reaction of unknown etiology associated with drug exposure and consistent with an immune phenomenon. Efforts should be made to rule out neoplastic, infectious, metabolic, toxin or other etiologic causes prior to labeling an event an irAEs. Serologic, immunologic, and histologic (biopsy) data should be used to support the diagnosis of an immune-related toxicity. Suspected immune-related adverse reactions must be documented on an AE or SAE form.

Patients should be informed of and carefully monitored for evidence of clinically significant systemic immune-mediated adverse reactions (e.g., systemic lupus erythematosus-like diseases) or organ-specific immune-mediated adverse reaction (e.g., rash, colitis, uveitis, hepatitis or thyroid disease). If an immune-mediated adverse reaction is noted, appropriate work-up (including biopsy if possible) should be performed, and steroid therapy may be considered if clinically necessary.

Recommended guidelines for specific immune-mediated adverse reactions are included in Appendix II. These recommendations should be utilized as clinically appropriate for the treatment of individual patients. Please contact the PI for any questions

12.2 DOSE DELAY CRITERIA:

Toxicity from Ipilimumab plus Nivolumab and Relatlimab plus Nivolumab will be graded by CTCAE v5.0. No dose reductions will occur for drug related adverse events but rather drug therapy will be held and next cycle delayed.

Subjects who experience the following must have all study drugs held:

Select drug-related AEs and drug-related laboratory abnormalities:

- \geq Grade 2 pneumonitis
- \geq Grade 2 elevation of liver tests (AST or ALT and/or total bilirubin)
- \geq Grade 2 increased creatinine
- \geq Grade 2 diarrhea or colitis
- \geq Grade 2 neurological AE
- \geq Grade 3 skin AE
- Myocarditis (any grade)
- All troponin elevations require a dose delay to allow for prompt cardiac evaluation. Following this evaluation, determination of further treatment will be based on the discretion of the PI.
- Grade 4 amylase and/or lipase abnormalities regardless of symptoms or clinical manifestations.
- Any adverse event, laboratory abnormality, or intercurrent illness which, in the judgment of the investigator, warrants delaying the dose of study medication.

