12.3 ADVERSE EVENT TREATMENT DISCONTINUATION CRITERIA

1. Any Grade ≥ 2 drug-related uveitis, eye pain or blurred vision that does not respond to topical therapy and does not improve to Grade 1 severity within the re-treatment period OR requires systemic treatment
2. Any Grade ≥ 3 non-skin, drug-related AE lasting > 7 days, or recurs with the following exceptions for laboratory abnormalities, diarrhea, colitis, neurologic toxicity, drug-related uveitis, pneumonitis, bronchospasm, hypersensitivity reactions, infusion reactions, and endocrinopathies:
 - a. Grade ≥ 3 drug-related myocarditis, diarrhea, colitis, neurologic toxicity, uveitis, pneumonitis, bronchospasm, hypersensitivity reaction, or infusion reaction of any duration requires discontinuation:-- Grade ≥ 3 drug-related endocrinopathies, adequately controlled with only physiologic hormone replacement do not require discontinuation. Adrenal insufficiency requires discontinuation regardless of control with hormone replacement.
 - b. Grade > 3 drug-related laboratory abnormalities do not require treatment discontinuation except:
 - i. Grade > 3 drug-related thrombocytopenia > 7 days or associated with bleeding requires discontinuation
 - c. Any drug-related liver function test (LFT) abnormality that meets the following criteria require discontinuation:
 - i. Grade > 3 drug-related AST, ALT or Total Bilirubin requires discontinuation*
 - ii. Concurrent AST or ALT $> 3 \times$ ULN and total bilirubin $> 2 \times$ ULN
- * In most cases of Grade 3 AST or ALT elevation, study treatment will be permanently discontinued. If the investigator determines a possible favorable benefit/risk ratio that warrants continuation of study treatment, a discussion between the investigator and the Sponsor
3. Any Grade 4 drug-related adverse event or laboratory abnormality (including but not limited to creatinine, AST, ALT, or Total Bilirubin), except for the following events which do not require discontinuation:
 - Grade 4 neutropenia ≤ 7 days
 - Grade 4 lymphopenia or leukopenia or asymptomatic amylase or lipase
 - Isolated Grade 4 electrolyte imbalances/abnormalities that are not associated with clinical sequelae and are corrected with supplementation/appropriate management within 72 hours of their onset

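### For concurrent AST/ALT and bilirubin rises, Section 12.3 requires discontinuation while the Appendix II hepatic footnote permits delay, and the protocol does not say which text governs

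*Combined protocol and SAP*

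**What the plan says.** Section 12.1 refers sites to the appendix for immune-mediated events: "Recommended guidelines for specific immune-mediated adverse reactions are included in Appendix II". It asks that they be applied as clinically appropriate. The footnote to the hepatic algorithm in Appendix II says "I-O therapy may be delayed rather than discontinued if AST/ALT" is at most 8 × ULN or total bilirubin is at most 5 × ULN. It does not mention Section 12.3 and does not treat combined rises separately.

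Section 12.3 item 2c is worded as a requirement: "Any drug-related liver function test (LFT) abnormality that meets the following criteria require discontinuation". Two criteria follow:

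- Item (i): "Grade > 3 drug-related AST, ALT or Total Bilirubin requires discontinuation". It carries an asterisk, whose note begins "In most cases of Grade 3 AST or ALT elevation, study treatment will be permanently discontinued" and goes on to describe possible continuation with a discussion between investigator and sponsor.
- Item (ii): "Concurrent AST or ALT $> 3 \times$ ULN and total bilirubin $> 2 \times$ ULN". It carries no asterisk and no exception.

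Section 9.2 uses the same pair of multiples for potential drug-induced liver injury. Its first element is ALT or AST above 3 × ULN. Its second is "Total bilirubin > 2 times ULN, without initial findings of cholestasis (elevated serum alkaline phosphatase"). Its third is that no other cause is immediately apparent. Section 9.1 requires such events to be handled as SAEs.

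**The concern.** The footnote and item 2c(ii) answer the same question, whether to hold or to stop, and over part of their range they give different answers. Two sites, or two clinicians at one site, could handle the same liver-test result differently, and each could cite the protocol. The range includes the combined rise that the protocol itself uses as the numeric core of its liver injury definition, so this is a poor place for two instructions.

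There is a smaller statistical link. The toxicity pausing rule in Section 15.3.2 is defined by reference to the Section 12.3 criteria, with pauses at 3 of 10, 5 of 20 and 7 of 30 patients. If the status of an event is unclear when it is managed, it should at least be clear when it is counted.

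**Working it through.** The plan gives no figure to reproduce here. The check is whether the two conditions can hold for the same patient, using only multiples of ULN printed in the protocol.

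Let *a* be the higher of AST and ALT, and *b* total bilirubin, both in multiples of ULN. The event is taken as drug-related.

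- Section 12.3 item 2c(ii), discontinuation required: *a* > 3 and *b* > 2.
- Appendix II footnote as printed, delay permitted: *a* ≤ 8 or *b* ≤ 5.
- Appendix II footnote on a stricter reading: *a* ≤ 8 and *b* ≤ 5.

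Setting item 2c(ii) against each reading:

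- Stricter reading: both texts apply when 3 < *a* ≤ 8 and 2 < *b* ≤ 5.
- Printed *or*: both texts apply to every patient meeting item 2c(ii), except those with *a* > 8 and *b* > 5 together.

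| *a* | *b* | Item 2c(ii) requires discontinuation | Footnote permits delay (*or*) | Footnote permits delay (*and*) |
|---|---|---|---|---|
| 3.5 | 2.5 | yes | yes | yes |
| 4 | 2.5 | yes | yes | yes |
| 6 | 2.5 | yes | yes | yes |
| 8 | 5 | yes | yes | yes |
| 8 | 12 | yes | yes | no |
| 25 | 4 | yes | yes | no |
| 9 | 6 | yes | no | no |
| 6 | 1 | no | yes | yes |

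The first four rows conflict on either reading. The next two conflict only if *or* is taken literally, so the word needs clarifying in its own right. In the seventh row only item 2c(ii) applies, so there is no conflict. The last row is an isolated rise that item 2c(ii) does not reach.

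For Section 9.2, *a* > 3 and *b* > 2 meet the numeric elements. The full definition also needs no initial cholestasis and no other apparent cause, so the overlap includes potential liver injury but is not the same as it.

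**The case against.** The best defence is that the protocol already ranks the two texts in substance. Appendix II calls itself general guidance for all immuno-oncology agents and regimens, Section 12.1 calls it recommended, and the footnote is permissive. Section 12.3 is mandatory, and Section 6.7 says treatment must be discontinued for unacceptable adverse events as set out in Section 12.0. The hepatic bullet under Section 12.3 item 7 lets a patient resume after a liver-test delay only if the permanent discontinuation criteria are not met. Section 12.2 holds all study drugs from Grade 2 liver-test elevations in any case. All of this stands and lowers the weight of the point. What it does not supply is a sentence saying that one text prevails, and the footnote speaks directly to the choice between delaying and stopping.

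A reader might infer more than the documents support:

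- *Re-dosing after a combined rise.* The item 7 bullet bars resumption for a patient who meets item 2c(ii). The footnote creates ambiguity but does not clearly authorise re-dosing.
- *A conflict for isolated high ALT, such as 15 × ULN with normal bilirubin.* This needs CTCAE cut-offs that the documents do not give. The hepatic algorithm figure is not available, so the entry carrying the asterisk cannot be seen. Section 12.3 also has its own limited route for Grade 3 AST or ALT through sponsor discussion.
- *About two affected patients.* Applying the 8.3% in Section 2.4.6 to 20 to 24 ipilimumab patients gives 0.083 × 20 = 1.7 to 0.083 × 24 = 2.0. That rate is for Grade 3 or 4 raised ALT alone in the cited melanoma trial, so it does not measure concurrent rises.
- *Delayed patients dropping out of the pausing rule.* Section 15.3.2 counts events sufficient to warrant discontinuation under Section 12.3. It does not count actual stops, so an event meeting item 2c(ii) counts even if the site only delayed.

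**Conclusion.** The inconsistency is real and follows from the printed thresholds alone. For a drug-related concurrent rise with AST/ALT above 3 and up to 8 × ULN and bilirubin above 2 and up to 5 × ULN, Section 12.3 requires discontinuation and Appendix II permits delay, on either reading of *or*. The literal *or* widens the overlap.

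The conclusion rests on two assumptions: the event is drug-related, and the footnote means what its own words say although its algorithm figure is not available. The guidance label and the cross-references in Sections 6.7 and 12.3 soften the conflict without resolving it. The number of patients affected cannot be given, because the documents contain no rate for concurrent rises. The point warrants correction because it concerns patient safety and is cheap to settle. It does not undermine the design or the primary analysis, and it implies no view on which liver rule is clinically right.

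**What to change.** Reconcile Section 12.3 item 2c, the hepatic bullet on resuming treatment under Section 12.3 item 7, and the Appendix II hepatic footnote, so that all three give the same instruction for concurrent liver-test rises. Clarify in the footnote whether *or* is meant literally. Add a sentence to Section 12.1 stating which text governs wherever Section 12.3 and Appendix II differ. In Section 15.3.2, confirm that an event meeting the Section 12.3 criteria counts toward Table 9 whether the site delayed or stopped treatment. The sponsor decides the clinical rule.

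The cost is one sentence in Section 12.1, one clause in Section 15.3.2 and aligned wording in the liver-test passages, with the usual notice of an amendment to the IRB. It adds no procedures, visits or patients.
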